13.3.2 Analysis of secondary efficacy variables

The secondary efficacy variables for this study are described in Section 4.1.2.

Subjects will be categorized as responders if the reduction in partial-onset seizure frequency from the Baseline Period to the appropriate treatment period meets the level specified in the given analysis. Response to treatment will be summarized for the proportion of subjects experiencing a $\geq 25\%$ to $< 50\%$, 50 to 75% , or $> 75\%$ reduction in partial-onset seizure frequency from the Baseline Period to the Maintenance Period. Proportion of subjects experiencing no change in partial-onset seizure frequency (ie, between $< 25\%$ reduction and $< 25\%$ increase in seizure frequency) and the proportion of subjects experiencing $\geq 25\%$

increase in partial-onset seizure frequency from the Baseline Period to the Maintenance Period will be presented. These response categories will also be presented from Baseline to the Treatment Period.

The difference in responder rate for 50% reduction in partial-onset seizure frequency between the LCM treatment group and placebo will be analyzed using a logistic regression model with effects for treatment and pooled center. No other statistical testing will be performed for the other secondary variables related to reduction in partial-onset seizure frequency.

The number and percentage of subjects experiencing a <50%, 50 to 75%, or >75% reduction in seizure frequency from Baseline to each post-Baseline visit will be presented by treatment group. The descriptive statistics for percent change in seizure frequency per 28 days from Baseline to each post-Baseline visit, the Maintenance Period, and entire Treatment and Maintenance Periods will be presented by seizure type and treatment group. No inferential testing will be performed for these summaries.

The change in seizure frequency per 28 days from Baseline to the Treatment Period, defined as the combined Titration and Maintenance Periods, will be summarized by treatment group (LCM or placebo) using descriptive statistics. Statistical testing will be performed using an ANCOVA model with terms for treatment and pooled center and Baseline seizure frequency as a covariate.

The change in seizure frequency by period will also be summarized using descriptive statistics by treatment group and seizure type.

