## 2.4 Determination of sample size

Assuming an effect size of 0.342, in which the effect size was calculated using a placebo-subtracted difference of -0.249 and a common SD of 0.73 on the log-transformed data, the difference of -0.249 on the log-transformed data is equivalent to approximately 22% reduction over placebo after exponentiation. With this effect size, power of 80%, and a 2-sided test at the 5% level of significance, a sample of 135 subjects in each treatment arm will be needed.

Assuming a responder rate of 22% and 40% for the placebo and LCM groups, respectively, a 2-sided continuity corrected Chi-square test at a significance level of 5% will provide approximately 87% power with 135 subjects in the placebo group and 135 subjects in the LCM group.

To account for an anticipated subject dropout rate of approximately 14%, the planned number of subjects to enroll is 154 subjects per treatment arm.

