## **4 STATISTICAL/ANALYTICAL ISSUES**

### **4.1 Adjustments for covariates**

An analysis of the primary efficacy variable and analyses of several other efficacy variables will be adjusted for Baseline seizure frequency and pooled center.

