### **8.1.2 Primary analysis of the primary efficacy variable**

Seizure frequency will be analyzed using analysis of covariance (ANCOVA) with terms for treatment and center (pooled appropriately), on log-transformed seizure frequency using the transformation of  $\ln(X+1)$ , where X is the seizure frequency. Log transformed Baseline seizure frequency will be used as a covariate. Assumptions for the parametric model will be evaluated by diagnostic (eg, Shapiro-Wilk test for normality) and graphical methods such as residual plots, including normal probability plots, histograms, and plots of residuals versus Baseline covariate values and treatment. An assessment will be made with regards to the influence of individual observations (eg, extreme outliers) on the analysis. To the extent feasible, such potential influential observations will be identified prior to unblinding, and an assessment will be made with regard to the potential impact of such data, including the evaluation of alternative statistical methodology such as non-parametric methods. If deemed that a non-parametric method is warranted, an ANCOVA model on rank of seizure frequency per 28 days with terms for treatment and center (pooled appropriately) will be employed as the primary analysis. Ranked seizure frequency per 28 days during the Baseline Period will be used as a covariate.

The seizure frequency between treatment and placebo will be compared using the least squares means (LSMs). The percent reduction over placebo will be estimated as  $100 \times (1 - \exp[\text{LSM}_{\text{LCM}} - \text{LSM}_{\text{placebo}}])$ . A 95% CI will also be calculated for the percent reduction over placebo.

Partial-onset seizure frequency per 28 days during the Baseline Period and during the Maintenance Period, and the change from Baseline will be summarized by treatment group. This summary will be repeated by treatment group and age group, using the levels defined in section 4.8.

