### **8.2.2 Proportion of responders, where a responder is a subject experiencing a 50% or greater reduction in partial-onset seizure frequency from Baseline to end of Maintenance Period**

The secondary efficacy variable is the proportion of responders, where a responder is a subject experiencing a 50% or greater reduction in partial-onset seizure frequency from Baseline to the end of Maintenance Period.

Percent reduction will be calculated as  $([\text{absolute reduction in partial-onset seizure frequency}] \div [\text{Baseline partial-onset seizure frequency}]) \times 100$ .

Absolute reduction in partial-onset seizure frequency is calculated as  $(\text{Baseline partial-onset seizure frequency}) - (\text{Maintenance Period partial-onset seizure frequency})$ .

The subject is considered a responder if the data shows a 50% or greater reduction in partial-onset seizure frequency from Baseline to end of Maintenance Period, otherwise the subject will be considered a non-responder.

This variable will be analyzed using a logistic regression model with terms for treatment and center to measure the association between the response variable and treatment after controlling for center. The odds ratio, 95% CI, and p-value associated with treatment will be presented.

The number and percentage of responders will be summarized by treatment group.

The response to treatment for each response level will also be summarized using descriptive statistics by treatment group and seizure type, with the seizure types presented as follows: simple partial seizures (IA), complex partial seizures (IB), partial seizures evolving to secondarily generalized (IC), generalized seizures (II), and unclassified epileptic seizures (III). This summary will be repeated by treatment group and age group, using the levels defined in section 4.8.

Only subjects who experienced the respective seizure type during the Baseline Period will be included in the analysis for that seizure type with only the seizure frequencies of that seizure type being used in the analysis. Subjects can be analyzed under multiple seizure types in these summaries. No statistical testing will be performed for these by seizure type summaries.

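### The 50% responder logistic model omits Baseline seizure frequency; adjusting for it would add a little power and protect against chance imbalance if Baseline predicts response, though the planned test is valid

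*SAP*

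**What the plan says.** SAP 8.2.2 calls a subject a responder if partial-onset seizure frequency falls by at least half from that subject's own Baseline. It fits a logistic model with "terms for treatment and center to measure the association between the response variable and treatment after controlling for center". Protocol 13.3.2 specifies a "logistic regression model with effects for treatment and pooled center". Neither has a Baseline term.

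For the primary ANCOVA, SAP 8.1.2 states: "Log transformed Baseline seizure frequency will be used as a covariate". SAP 8.2.1 also adjusts the Treatment Period comparison for Baseline frequency. SAP 4.1 says that an analysis of the primary variable and analyses of "several other efficacy variables will be adjusted for Baseline seizure frequency and pooled center".

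The responder rate is the only secondary variable with a stated power. SAP 2.4 begins "Assuming a responder rate of 22% and 40% for the placebo and LCM groups, respectively", applies a two-sided 5% chi-square test with continuity correction, and concludes that it "will provide approximately 87% power with 135 subjects in the placebo group and 135 subjects in the LCM group". SAP 4.5 makes no multiplicity adjustment, and the documents do not rank the secondary variables.

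**The concern.** Defining response relative to Baseline does not by itself remove Baseline as a predictor. Write ln M = a + b ln B + e, where M is Maintenance and B is Baseline frequency. Then ln(M/B) = a + (b − 1) ln B + e. The chance of a 50% reduction is free of B only if b = 1. If b is below 1, as regression to the mean would produce, subjects with high Baseline counts respond more often. Selection favours this: protocol 6.1 requires a minimum seizure history and at least 2 seizures in the prospective Baseline. The primary ANCOVA estimates the slope and does not fix it at 1.

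The documents describe stratification by age category only (protocol 5.1.2, SAP 2.3), so nothing in the stated randomization balances Baseline frequency. At stake are a small amount of power and the robustness of the responder odds ratio if the arms differ at Baseline by chance.

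**Working it through.** **Inputs from SAP 2.4:** responder rates 22% and 40%, 135 per arm, two-sided 5%. **Not in the documents:** how strongly Baseline predicts response. This is assumed below and shown as a range.

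**1. The plan's own figure.** Mean rate 0.31.
- SE under the null = √(2 × 0.31 × 0.69 / 135) = 0.0563.
- SE under the alternative = √((0.22 × 0.78 + 0.40 × 0.60) / 135) = 0.0552.
- Power = Φ[(0.18 − 1/135 − 1.96 × 0.0563) / 0.0552] = Φ(1.13) = 87.0%.

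The stated 87% reproduces for an unadjusted test. Without the continuity correction it is 89.6%, which is why the simulated logistic tests below start near 90%.

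**2. Power with and without a Baseline covariate.** Simulated trials had 135 per arm, marginal rates 22% and 40%, and 10,000 trials per row, with no center term. Here ρ is the assumed correlation of log Baseline frequency with the latent response.

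| ρ | Unadjusted | Adjusted | Gain (points) |
|---|---|---|---|
| 0 | 89.1% | 89.1% | 0 |
| 0.1 | 90.3% | 90.6% | 0.3 |
| 0.2 | 89.4% | 90.1% | 0.7 |
| 0.3 | 90.1% | 91.6% | 1.5 |
| 0.5 | 89.2% | 93.5% | 4.3 |

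The marginal rates are fixed, so the unadjusted column varies only by simulation error. Illustrative count models (median 6 to 15 seizures per 28 days, 8-week Baseline, 10-week Maintenance) gave ρ from about −0.08 to 0.31, so the last row lies outside the range they support.

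A second simulation used lognormal rates and Poisson counts over 56 and 70 days, with 5,000 trials per setting. Power went from 90.3% to 90.2% at slope 0.93, from 89.7% to 90.0% at 0.84, and from 89.4–89.7% to 90.6–90.7% at 0.75–0.76. At slope 0.75, placebo response was 14% in the lowest Baseline quarter and 33% in the highest.

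**3. Chance imbalance.** The SE of the between-arm Baseline difference is √(2/135) = 0.122 SD.
- At slope 0.75 the simulated Baseline coefficient was 0.461 per SD. A 2-SE imbalance shifts the log odds ratio by 0.461 × 2 × 0.122 = 0.11.
- Planned log odds ratio: ln[(0.40/0.60) / (0.22/0.78)] = 0.86. The shift is 0.11/0.86 = 13% of it.
- SE of the log odds ratio: √(1/29.7 + 1/105.3 + 1/54 + 1/81) = 0.27. The shift is about 0.4 SE.
- On the risk scale, with a true rate of 31% in both arms, an imbalance at the 95% limit (1.96 × 0.122 = 0.239 SD) creates a spurious difference of 0.8, 1.7 and 2.5 points at ρ = 0.1, 0.2 and 0.3, against the planned 18.

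**4. Validity.** Overall simulated type I error of the unadjusted test was 4.3% to 5.1%. Among trials with imbalance beyond the 95% limit it was 6.0% unadjusted v 4.3% adjusted at ρ = 0.3, and 13.1% v 5.4% at ρ = 0.5. These conditional rates rest on about 500 trials each, so the ρ = 0.3 contrast is only suggestive.

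**5. Where the power comes from.** In a count model at slope 0.75 (median 8 per 28 days), adjustment raised the mean SE from 0.274 to 0.284 and moved the log odds ratio from 0.875 to 0.926. The ratio went from 0.875/0.274 = 3.19 to 0.926/0.284 = 3.26. The gain comes from a larger, conditional odds ratio and not from a smaller SE.

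**The case against.** The protocol and SAP agree on the model, randomization makes the unadjusted test valid, and the endpoint is already scaled to each subject's Baseline. The benefit depends on a slope that neither document gives, and it may be nil. The slope-0.75 case is not anchored by the planning figures. SAP 2.4 gives "a placebo-subtracted difference of -0.249 and a common SD of 0.73 on the log-transformed data" without saying that the SD is Baseline-adjusted, and a residual SD would not identify a slope anyway. Forcing 22% v 40% at that slope needed a log effect of about −0.43, well beyond the planned −0.249. A 2-SE imbalance occurs in only about 5% of trials, counting both directions. All of this stands. It limits the size of the point but does not argue against pre-specifying the covariate.

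A reader might infer more than the documents support:
- **That SAP 8.2.2 contradicts SAP 4.1.** It does not; 4.1 speaks of several other variables, not all.
- **That the 87% power is wrong or assumed adjustment.** Step 1 shows otherwise.
- **That precision is lost.** In logistic regression, adjustment does not shrink the SE of the log odds ratio (step 5).
- **That the logistic models in SAP 8.2.5 and 8.2.6 need the same term.** No power calculation supports this. The no-change category is a two-sided window that need not be monotone in Baseline, and protocol 13.3.2 excludes testing of these variables.

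**Conclusion.** The omission is certain and its consequence is modest. The planned responder test is valid, and no figure in the plan needs correction. If Baseline predicts response, leaving it out costs 0 to about 1.5 points of power for correlations up to 0.3. It also leaves the odds ratio open to a shift of up to about 0.11 on the log scale (about 0.4 SE) under a 2-SE imbalance at an assumed slope of 0.75. With a slope near 1 there is essentially no gain. This is an improvement in efficiency and robustness for SAP 8.2.2 only. It is worth making because the covariate is already in hand, and because settling it before unblinding avoids a post hoc adjusted analysis if the arms prove uneven.

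**What to change.** Before unblinding, amend SAP 8.2.2 so that the logistic model contains treatment, pooled center and ln(Baseline partial-onset seizure frequency per 28 days + 1), the same transformation as in the primary ANCOVA. Report the odds ratio with its 95% CI and p-value, and state in the table footnote that it is conditional on Baseline. Keep the treatment-and-center model as a pre-specified sensitivity analysis. Record the departure from protocol 13.3.2 in SAP 3.9, which at present declares no changes.

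The cost is one covariate in the program, a conditional odds ratio in place of one adjusted for center only, and documentation of the change; the sponsor should judge whether protocol 14.5 also calls for an amendment. No data are lost, because responder status cannot be computed without Baseline.

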### **8.2.3 Proportion of subjects experiencing a $\geq 25\%$ to $< 50\%$ , 50% to 75%, or $> 75\%$ reduction in partial-onset seizure frequency from Baseline to end of Maintenance Period**

The proportion of subjects experiencing a  $\geq 25\%$  to  $< 50\%$ , 50% to 75%, or  $> 75\%$  reduction in partial-onset seizure frequency from Baseline to end of Maintenance Period will be summarized by treatment group.

Percent reduction will be calculated as defined in section 8.2.2.

The number and percentage of subjects in each of the categories will be summarized by treatment group.

### **8.2.4 Proportion of subjects experiencing a $\geq 25\%$ to $< 50\%$ , 50% to 75%, or $> 75\%$ reduction in partial-onset seizure frequency from Baseline to entire Treatment Period**

The secondary efficacy variable is the proportion of subjects experiencing a  $\geq 25\%$  to  $< 50\%$ , 50% to 75%, or  $> 75\%$  reduction in partial-onset seizure frequency from Baseline to the entire Treatment Period.

Percent reduction will be calculated as defined in section 8.2.2.

The number and percentage of subjects in each of the 3 categories will be summarized by treatment group.

Additionally, the proportion of subjects experiencing a  $\geq 25\%$  to  $< 50\%$ , 50% to 75%, or  $> 75\%$  reduction in partial-onset seizure frequency from Baseline to each post-Baseline scheduled visit during the entire Treatment Period will be determined.

Percent reduction will be calculated as defined in section 8.2.2, with absolute reduction in partial-onset seizure frequency calculated as (Baseline partial-onset seizure frequency) minus (Visit partial-onset seizure frequency).

Each subject will be categorized into 1 of the 3 reduction in partial-onset seizure groups ( $\geq 25\%$  to  $< 50\%$ , 50% to 75%, or  $> 75\%$ ), at each visit.

The number and percentage of subjects in each of the 3 categories will be summarized by treatment group for each post-Baseline visit.

### **8.2.5 Proportion of subjects experiencing no change in partial-onset seizure frequency from Baseline to entire Treatment Period**

The secondary efficacy variable is the proportion of subjects experiencing no change in partial-onset seizure frequency (between <25% reduction and <25% increase) from Baseline to the entire Treatment Period.

Percent reduction/increase will be calculated as defined in section 8.2.2.

Each subject will be categorized into 1 of the 2 partial-onset seizure frequency groups (between <25% reduction and <25% increase, or not between <25% reduction and <25% increase).

This variable will be analyzed using a logistic regression model with terms for treatment and center to measure the association between the response variable and treatment after controlling for center. The odds ratio, 95% CI, and p-value associated with treatment will be presented.

The number and percentage of subjects in each of the 2 categories will be summarized by treatment group.

### **8.2.6 Proportion of subjects experiencing an increase in partial-onset seizure frequency from Baseline to entire Treatment Period**

The secondary efficacy variable is the proportion of subjects experiencing an increase in partial-onset seizure frequency of  $\geq 25\%$  from Baseline to the entire Treatment Period.

Percent increase will be calculated as defined in section 8.2.2.

Each subject will be categorized in 1 of 2 increase in partial-onset seizure frequency groups ( $\geq 25\%$  or <25%).

This variable will be analyzed using a logistic regression model with terms for treatment and center to measure the association between the response variable and treatment after controlling for center. The odds ratio, 95% CI, and p-value associated with treatment will be presented.

The number and percentage of subjects in each of the 2 categories will be summarized by treatment group.

### **8.2.7 Change in partial-onset seizure frequency per 28 days from Baseline to the entire Treatment Period by seizure type**

The partial-onset seizure frequency per 28 days will be calculated for both the Baseline Period and for the entire Treatment Period, as detailed in section 8.1.1, by seizure type. The change from Baseline will also be calculated by seizure type.

The change in partial-onset seizure frequency per 28 days from Baseline to the entire Treatment Period will be analyzed as detailed in Section 8.1.2.

Partial-onset seizure frequency per 28 days during the Baseline Period and during the entire Treatment Period, and change from Baseline will be summarized by treatment group and seizure type.

In addition, descriptive statistics for change and percent change in seizure frequency per 28 days from Baseline to each post-Baseline visit during the entire Treatment Period will be presented by treatment group and seizure type. Partial-onset seizure frequency per 28 days will be presented

graphically at each visit by treatment group, and separately at each visit by seizure type and treatment group.

### **8.2.8 Proportion of seizure-free days during Maintenance Period**

For all subjects who enter the Maintenance Period, the proportion of seizure-free days during the Maintenance Period will be calculated.

The proportion of seizure-free days will be calculated as (days with number of seizures = 0 during the Maintenance Period) divided by (days with recorded data in the subject diary during the Maintenance Period), where “days with recorded data in the subject diary” excludes any days where “Not Done” is recorded.

Days with missing seizure diary information will be excluded from both the numerator and denominator for the seizure-free days calculation.

For all subjects who complete the Maintenance Period, the proportion of seizure-free days during the Maintenance Period will be calculated as described above, and summarized descriptively by treatment group.

Statistical testing for the proportion of seizure-free days during the Maintenance Period will be based on an ANCOVA model with terms for treatment and pooled site and a covariate of the proportion of seizure-free days during the Baseline Period. Only Subjects with efficacy data collected during the Maintenance Period will be included.

The proportion of seizure-free days during the Maintenance Period will also be summarized using descriptive statistics by treatment group and seizure type.

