4.1.2 Secondary efficacy variables

The secondary efficacy variables are described below:

- Proportion of responders, where a responder is a subject experiencing a 50% or greater reduction in partial-onset seizure frequency from Baseline to the Maintenance Period
- Proportion of subjects experiencing a $\geq 25\%$ to $< 50\%$, 50% to 75%, or $> 75\%$ reduction in partial-onset seizure frequency from Baseline to the end of Maintenance Period
- Change in partial-onset seizure frequency per 28 days from Baseline to the entire treatment (ie, Titration+Maintenance Periods)
- Proportion of subjects experiencing a $\geq 25\%$ to $< 50\%$, 50% to 75%, or $> 75\%$ reduction in partial-onset seizure frequency from Baseline to the entire treatment (ie, Titration+Maintenance Periods)
- Proportion of subjects experiencing no change in partial-onset seizure frequency (between $< 25\%$ reduction and $< 25\%$ increase) from Baseline to the entire treatment (ie, Titration+Maintenance Periods)
- Proportion of subjects experiencing an increase in partial-onset seizure frequency of $\geq 25\%$ from Baseline to the entire treatment (ie, Titration+Maintenance Periods)
- Change in partial-onset seizure frequency per 28 days from Baseline to the entire treatment (ie, Titration+Maintenance Periods) by seizure type
- Proportion of seizure-free days during the Maintenance Period for subjects who entered the Maintenance Period

- Proportion of subjects who achieved “seizure-free” status (yes/no) for subjects who completed the Maintenance Period

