For subjects who enter the Maintenance Period, proportion of seizure-free days during the Maintenance Period will be calculated and summarized by treatment group descriptively.

For subjects who complete the Maintenance Period, the number and percentage of subjects who achieved "seizure-free" status during the Maintenance Period will be tabulated and presented by treatment group descriptively.

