#### **4.2.5 Incomplete dates for seizure diary data**

Seizure frequency and seizure-free days will be calculated over non-missing diary days during each time interval; days for which seizure diary data were not obtained will not be considered in the calculation of seizure frequency or seizure-free days. If more than 10% of the diary entries are missing for a specific subject and time interval, then that subject will not be considered for the calculation of seizure frequency or seizure-free days during that time interval.

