## **8.2 Statistical analysis of the secondary efficacy variables**

The secondary efficacy variables will be summarized and/or analyzed for the FAS.

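### SAP 8.2.8 attaches the overall by-treatment summary of seizure-free days to Maintenance completers, whereas the protocol and the SAP's own variable list specify subjects who enter Maintenance

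*SAP*

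**What the plan says.** Protocol 4.1.2 lists the variable as "Proportion of seizure-free days during the Maintenance Period for subjects who entered the Maintenance Period", and SAP 2.2.1.2 repeats that definition. Protocol 13.3.2 gives the analysis: "For subjects who enter the Maintenance Period, proportion of seizure-free days during the Maintenance Period will be calculated and summarized by treatment group descriptively". It plans no test for this variable.

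SAP 8.2.8 contains four statements that bear on who is analysed:

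- It begins with entrants: "For all subjects who enter the Maintenance Period, the proportion of seizure-free days during the Maintenance Period will be calculated". That sentence orders no summary.
- It turns to completers: "For all subjects who complete the Maintenance Period, the proportion of seizure-free days during the Maintenance Period will be calculated as described above". The descriptive summary by treatment group follows in this same sentence.
- It adds an ANCOVA with the Baseline proportion of seizure-free days as covariate, limited as follows: "Only Subjects with efficacy data collected during the Maintenance Period will be included".
- It ends with a table that "will also be summarized using descriptive statistics by treatment group and seizure type", without naming a population.

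Two general rules also apply. SAP 8.2 says "The secondary efficacy variables will be summarized and/or analyzed for the FAS". SAP 4.2.5 removes a subject from the calculation for an interval under this condition: "If more than 10% of the diary entries are missing for a specific subject and time interval". SAP 3.9 reports no departures from the protocol's analyses.

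**The concern.** A programmer who follows SAP 8.2.8 literally will produce the overall by-arm table for completers. The table that protocol 13.3.2 asks for, covering everyone who enters Maintenance, is not ordered anywhere in that section.

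The subjects lost are those who enter Maintenance and then withdraw. They are not an arbitrary group. Protocol 5.1 and 7.2.2 withdraw subjects who need a change of study dose during Maintenance, and protocol 6.3 lists other compulsory reasons, among them intolerable adverse events, convulsive status epilepticus, excess rescue medication and a need to alter background AED dose. These reasons arise after randomisation and may depend on treatment. A completers-only mean is therefore open to selection in a way that the protocol's summary is not.

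There is also a mismatch within the report. The ANCOVA keeps Maintenance withdrawers who have diary data, so the p-value and the descriptive means beside it would describe different subjects.

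**Working it through.** No figure in the documents tests this point directly. The check is a comparison of texts, followed by an illustration of size.

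**Step 1: set the populations side by side.**

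| Place | Output | Population |
|---|---|---|
| Protocol 4.1.2, SAP 2.2.1.2 | definition of the variable | entrants |
| Protocol 13.3.2 | descriptive summary by arm | entrants |
| SAP 8.2.8 | calculation only | entrants |
| SAP 8.2.8 | descriptive summary by arm | completers |
| SAP 8.2.8 | ANCOVA | subjects with Maintenance efficacy data |
| SAP 8.2.8 | summary by seizure type | not stated |

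The same output, the descriptive summary by arm, has different populations in the two documents.

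**Step 2: is the difference incidental?** The protocol uses the two terms with care. In 4.1.2 and 13.3.2 it takes entrants for seizure-free days and completers for seizure-free status. SAP 8.2.9 keeps completers for the status variable, as the protocol does. SAP 8.2.8 applies the completer condition to the variable that the protocol sets for entrants.

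**Step 3: is completion needed to compute the measure?** No. SAP 8.2.8 divides zero-seizure days by recorded diary days, and SAP 3.2.2 ends the Maintenance Period at the Early Termination Visit for a subject who withdraws during it. A partial period gives a valid proportion, subject to the 10% missing-diary rule in SAP 4.2.5.

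**Step 4: size.** The inputs are 154 subjects per arm and 14% dropout (protocol 13.8), and the 24% ceiling on the dropout rate (protocol 13.7). The plan's 154 is reproduced by 135 × 1.14 = 153.9. The share *s* of dropouts that occur in Maintenance is not given, so 25% to 100% is assumed. N is held at 154 for both rates.

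- Omitted per arm = 154 × d × s
- Entrants per arm = 154 − 154 × d × (1 − s)

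| d | s | Omitted | Entrants | Omitted / entrants |
|---|---|---|---|---|
| 14% | 25% | 5.4 | 137.8 | 3.9% |
| 14% | 50% | 10.8 | 143.2 | 7.5% |
| 14% | 100% | 21.6 | 154.0 | 14.0% |
| 24% | 25% | 9.2 | 126.3 | 7.3% |
| 24% | 100% | 37.0 | 154.0 | 24.0% |

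**Step 5: what this could do to one arm's mean.** The completer mean minus the entrant mean equals the omitted fraction times the difference between completers and withdrawers. Suppose the two groups differ by 0.10 to 0.20 in either direction (assumed). At 14% dropout the arm mean then shifts by 0.10 × 0.039 = 0.004 up to 0.20 × 0.140 = 0.028. At 24% it shifts by 0.10 × 0.073 = 0.007 up to 0.20 × 0.240 = 0.048. The completer mean is too high if withdrawers do worse and too low if they do better.

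**The case against.** The best defence is that SAP 8.2.8 is loosely written and records no decision to drop entrants. SAP 2.2.1.2 keeps the entrant definition, SAP 8.2 puts secondary variables on the FAS, SAP 3.9 says nothing has changed, and 8.2.8 itself opens with entrants. A reader could supply the missing summary from these. That is fair as to intent, but none of these places orders an entrants summary by arm, and the seizure-type table is a different output. The specific instruction still names completers.

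Three stronger readings are tempting, and the documents do not support them.

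- *The section uses three truly separate populations.* The ANCOVA condition amounts to entrants with usable Maintenance diary data, since the proportion cannot be computed otherwise. It differs from all entrants only by those without such data. The test is therefore close to the protocol's population, and the misplaced element is the completers-only summary.
- *The summary will favour the arm with more withdrawals.* That requires withdrawers to have fewer seizure-free days than completers. Some withdrawal reasons in protocol 6.3, such as ECG or liver findings, pregnancy or unwillingness to continue, say nothing about seizure control, and a needed dose change does not imply poor control either. The documents also give no dropout by arm.
- *About 11 subjects per arm will be lost.* That figure is one point on an assumed range. The 14% is an overall study rate with no split by period.

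It is also true that the stakes are modest: completer selection does not enter the p-value, and this is a secondary variable that the protocol treats descriptively.

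**Conclusion.** The point stands as an inconsistency between SAP 8.2.8 and both the protocol and SAP 2.2.1.2. Followed as written, the SAP reports the overall by-arm summary for the wrong population, does not declare the change in SAP 3.9, and sets that summary beside a test on a different group.

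The summary would leave out about 5 to 22 entrants per arm at the planned 14% dropout, or about 9 to 37 at the 24% ceiling. Both ranges rest on 154 per arm and on the assumed 25% to 100% share of dropouts in Maintenance. Bias in the arm means is possible if withdrawers differ from completers; its direction and any effect on the between-arm comparison are unknown. The primary analysis is untouched. This is a minor correction, worth making because it is clear-cut and nearly free.

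A related gap is that protocol 13.3.2 plans this variable descriptively. Protocol 13.2 allows inference for selected secondary variables, but the protocol does not name this one. The ANCOVA is thus an addition that SAP 3.9 should record.

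**What to change.** In SAP 8.2.8:

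1. State that the by-treatment descriptive summary covers all FAS subjects who enter the Maintenance Period and have diary data for it, subject to SAP 4.2.5.
2. State that the ANCOVA and the seizure-type table use that same set.
3. If a completers-only summary is kept, label it supplementary.

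In SAP 3.9, declare the ANCOVA for this variable as an addition to the protocol. If the sponsor prefers completers for the main summary, that must be declared and justified there too.

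The cost is a short rewrite of one section, one entry in SAP 3.9 and a changed population flag in the affected tables, all before unblinding. No new data are needed.
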